## **16.7 Serious Adverse Event Reporting**

An SAE is defined as any event that:

- Results in death (including suicide)
- Is life-threatening
- Results in hospitalization or prolongation of existing inpatient hospitalization
  - Planned admissions for respite care are not to be considered an SAE (the Medical Monitor should be contacted for confirmation regarding whether or not an admission for respite care should be considered planned or unplanned).

Unplanned admissions for respite care will constitute an SAE unless it is as a result of study partner needs that are independent of the subject's condition.

- An admission or prolongation of existing hospitalization because the subject does not want to be discharged, or because the study partner is unable or unwilling to care for the subject, is not to be considered an SAE.
- Admissions to a hospital that were planned or anticipated before the start of the study for an unrelated pre-existing medical condition are not to be considered an SAE.
- Results in persistent or significant disability or incapacity
- Is a congenital anomaly or birth defect
- Important medical events that might not be immediately life-threatening or result in death or hospitalization but might jeopardize the subject or might require intervention to prevent one of the other outcomes listed above. Examples of such events are intensive treatment in an emergency room or at home for allergic bronchospasm, blood dyscrasias or convulsions that do not result in hospitalization, or development of dependency or abuse

Medical and scientific judgment should be exercised in deciding whether an event is serious and whether expedited reporting is appropriate in other situations, such as important medical events that may not be immediately life-threatening or result in death or hospitalization but may jeopardize the subject or may require intervention to prevent one of the outcomes listed in the definitions above.

All SAEs must be reported on the eCRF. An assessment should be made by the investigator as to whether the event is study drug-related, *i.e.*, is 'causally' related to the study drug.

All SAEs (including any SAEs associated with COVID-19 that occur during study participation) should be reported to the Sponsor designee, Syneos Health, immediately (and not exceeding 24 hours following knowledge of the event). These should be followed by follow-up reports as soon as possible, whether or not the events are deemed study drug-related.

SAEs must be reported by entering the SAE information in the AE/SAE Section of the eCRF system. The information provided in the eCRF system should be as complete as possible, but must contain the following minimum fields:

- Subject number
- Brief description of the SAE (diagnosis or signs/symptoms)
- Serious criteria
- Causality assessment
- Assessment of the intensity of the event

Syneos Health Drug Safety will receive notification of the initial SAE *via* an e-mail alert generated from the eCRF system. In the event of any temporary disruption of the electronic system, an alternative SAE reporting mechanism will be available to site personnel; in this instance, a paper SAE report form will be available. Site personnel will complete the paper SAE report form, scan, and e-mail it within 24 hours to the following e-mail address:

[[contact]](mailto:[contact])

[contact]

Address:

Syneos Health  
Safety/Pharmacovigilance Department  
[name]  
United Kingdom

SAEs that are ongoing should be followed until resolved or stabilized to a level acceptable to the investigator.

SAEs reported after screen failure will not be recorded for the study. Emergent SAEs up to the point of screen failure will be followed up to resolution at the discretion of the PI.

The investigator is obliged to provide additional information as requested by the Medical Monitor. In general, this will include a description of the event in sufficient detail to allow for a complete medical assessment of the case and independent determination of possible causality. In the case of a subject death, a summary of available autopsy findings, if performed, must be submitted as soon as possible to Syneos Health. However, any supporting information provided should not reveal a subject's identity beyond the agreed study identifier. The investigator should ensure that information reported is accurate and consistent.

Information not available at the time of the initial report (*e.g.*, an end date for the AE, laboratory values received after the report, or hospital discharge summary) must be documented on a follow-up form. All follow-up information must be reported in the same timelines as initial information.

Any SAEs considered related to the study drug and discovered by the investigator after the study should be communicated in writing to the Sponsor within 24 hours following knowledge of the event.

## **16.8 Suspected, Unexpected Serious Adverse Reactions and Emerging Safety Information**

Suspected, unexpected serious adverse reactions are AEs that are believed to be related to an investigational medicinal product and are both unexpected (*i.e.*, the nature or severity is not expected from the information provided in the Investigator's Brochure) and serious. As stated in the EU 'CT-3' Communication from the Commission (2011/C 172/01) and the US Code of Federal Regulations (21 CFR 312.32), for there to be a reasonable possibility of a causal relationship between the event and study drug there must be facts (evidence) or arguments to suggest a causal relationship. Final assessment of expectedness for purposes of regulatory reporting is the responsibility of the Sponsor.

It is the responsibility of the Sponsor to determine whether a reported SAE fits the classification of a SUSAR and to notify the investigator of the decision as soon as possible.

All SUSAR reporting, whether determined following unblinding during study conduct or apparent only after the study has ended, will adhere to European Directives 2001/20/EC, 21 CFR 312.32 of the U.S. Code of Federal Regulations, Health Canada Food and Drug Regulation C.05.014, and other regions as applicable.

## 16.9 Malignancies

All cases of malignancies, other than non-melanoma skin cancers, are to be reported to the Sponsor designee, Syneos Health, as outlined above in Section 16.7. Adverse events of malignancies other than non-melanoma skin cancers are to be reported regardless of causality or whether they meet the criteria for serious. These will be reported to Health Canada as Adverse Drug Reactions (ADRs). Expedited reporting in other countries will be consistent with the handling of SUSARs.

## 16.10 Reporting of Pregnancy

Pregnancy is to be considered an immediately reportable event. This includes pregnancy of a female subject or a female sexual partner of a male subject. An event of a pregnancy will be reported to the Sponsor designee, Syneos Health, immediately (and not exceeding 24 hours following knowledge of the event), and followed by follow-up reports as soon as possible.

Subjects who become pregnant during the clinical study should discontinue study drug immediately and contact the investigator. Subjects should be instructed to notify the investigator of a pregnancy either during the Treatment period of the study or within 90 days after the last dose of study drug. Whenever possible, a pregnancy should be followed to term, any premature terminations reported, and the status of the mother and child reported to the Sponsor after delivery.

Although the pregnancy is not considered to be an AE or SAE, any pregnancy complications should be recorded as AEs or SAEs (if applicable). Any pregnancy should be followed through delivery for observation of any SAE, if possible. Therefore, regardless of whether or not a pregnancy is actually considered an SAE, a pregnancy form should be completed for all pregnancies.

The information provided in the eCRF should be as complete as possible, but must contain the following minimum fields:

- Subject number
- Confirmation that the subject's contact information is on file at the site
- Date of report of pregnancy
- Expected delivery date

All data related to pregnancy, pregnancy outcome, and SAEs associated with pregnancy should be recorded in a safety database maintained by personnel responsible for pharmacovigilance at Syneos Health. Pregnancies should initially be reported in the Pregnancy Notification Form, Part I and sent by e-mail to the e-mail address provided below. When the outcome of the pregnancy is known, site personnel will complete the Pregnancy Notification Form, Part II and e-mail it to the same e-mail address noted below.

Syneos Health Drug Safety will receive notification of the pregnancy *via* an e-mail alert generated from the eCRF system. In the event of any temporary disruption of the electronic system, site personnel will scan and e-mail a written report within 24 hours to the following e-mail address:

[[contact]](mailto:[contact])

[contact]

Address:

Syneos Health  
Safety/Pharmacovigilance Department  
[name],  
Farnborough,  

## **16.11 Guidance for the Handling of Adverse Events of Special Interest and Selected Test Abnormalities**

The pre-specified AESIs in this study are hemolytic anemia and lens discoloration. Guidelines for the monitoring and management of the AESIs are given below along with selected test abnormalities. Clinical circumstances requiring additional evaluation of a subject and/or potential interruption or discontinuation of study drug are presented.

### ***16.11.1 Hemolytic Anemia***

When there are signs and/or symptoms of clinically evident hemolytic anemia, dosing should be interrupted. A hemolysis panel should be considered (including complete blood count with differential, reticulocyte count [including absolute reticulocyte number], lactate dehydrogenase (LDH), direct and indirect bilirubin, and haptoglobin). See Section 13.8 for guidance on vitamin B12. If confirmed as related to study drug, dosing should be discontinued.

Signs of possible treatment-emergent hemolytic anemia include:

- Decrease by 20% from screening in red blood cell (RBC) count and/or hemoglobin
- Abnormal RBCs in peripheral blood smear
- Elevation of reticulocyte count to above laboratory normal range
- Increase in LDH or indirect bilirubin, or lower haptoglobin than screening

### ***16.11.2 Lens Discoloration***

For subjects with a history of lens implants, ophthalmological examinations (slit lamp examinations) will be performed prior to the first dose of study drug (during Screening or as part of Baseline assessments), at Visit 7, and at Visit 10 / early termination as scheduled procedures. Subjects and investigators are informed of the potential for lens discoloration in the Informed Consent Form and Investigator's Brochure, respectively. If a lens discoloration is identified by slit lamp examination, this is to be recorded as an AESI in the AE eCRF; however, no specific action is required for the study drug. Slit lamp examination should also be performed if a subject has cataract surgery / lens implantation at any point during his or her study participation (as soon as possible after the surgery), as well as in response to visual complaints if suggestive of lens discoloration.

### ***16.11.3 Other Safety Reasons Requiring Discontinuation of Study Drug***

If the calculated creatinine clearance is <30 mL/min and renal concerns arise, study drug should be discontinued.

For any other safety concerns that may arise during treatment, the Medical Monitor or 24-hour medical contact number (see Section 4) should be contacted to discuss possible discontinuation of study drug.

## 16.12 Urgent Safety Measures

The Sponsor and investigator may take appropriate urgent safety measures in order to protect the subjects of the clinical study against any immediate hazard to their health or safety.

The Sponsor and the Medical Monitor or designated deputy will be notified of any urgent safety measures taken by the investigator or qualified designee and advised of their responsibility to notify the licensing authority. The investigator or qualified designee will notify the Independent Ethics Committee/Institutional Review Board (IEC/IRB).

If these measures are taken, the Sponsor or investigator shall immediately give written notice to the pertinent regulatory authorities consistent with the regional/national requirements, IEC/IRB, and DSMB of the measures taken and the circumstances giving rise to those measures. In any event, the written notice shall be no later than 7 days from the date the measures are taken.

## 17 STATISTICAL ANALYSIS

A SAP will be finalized and signed off prior to database lock and unblinding. The SAP will provide details about the planned analysis. A brief overview of the plans for the primary analysis and selected secondary and exploratory analyses is given in the following sections. Specific ROI and SPM techniques and comparisons to previous Phase 3 data or external databases as well as Population PK analyses will be described in the SAP or a corresponding additional SAP where necessary; the SAP will provide details.

Changes to the planned analysis will be documented in the SAP prior to database lock and unblinding. Deviations from the SAP (if any) will be noted in the clinical study report.

The primary target of estimation is the difference in ADAS-cog11 and ADCS-ADL23 over 52 weeks in subjects receiving the LMTM dose of 16 mg/day as compared to placebo.

The primary efficacy analyses for FDA will be performed on the Efficacy Modified Intent-to-Treat (E-MITT) which will include all randomized subjects who took at least one dose of study drug and have a baseline and a valid post-baseline efficacy assessment, and for EMA on the Intent-to-Treat (ITT) population with conservative assumptions about disease progression made for subjects who have missing post-baseline assessments. Subjects will be analyzed in the treatment group and according to the stratification variables to which they were randomized.

Changes from baseline to Week 52 on the co-primary efficacy endpoints and other modalities with repeated measures such as MRI will be analyzed using a linear mixed model for repeated measures with unstructured covariance matrix (this assumption about the covariance matrix might be relaxed if the model does not converge; the SAP will provide details). The linear mixed model will contain fixed effects for time, treatment, and a treatment-by-time interaction; additionally, the baseline value of the corresponding endpoint will be included as a covariate and the randomization stratification variables of prior usage of AChEIs and/or

memantine, MMSE split (16-19, 20-25 or 26-27) as determined at Screening, and region will be included as fixed effects in the model. F-FDG-PET and other modalities with only one planned post-baseline assessment will be analyzed using an ANCOVA; the covariates for this model will be adjusted accordingly by removing terms with time.

Several of the analyses described below will be performed separately for the comparisons of LMTM 16 mg/day with placebo and 8 mg/day with placebo. As only the LMTM 16 mg/day and placebo comparison is a primary endpoint, the models will use two treatment levels dependent on the comparison of interest. Several analyses provided for the comparisons of LMTM 16 mg/day and placebo will be repeated for the LMTM 8 mg/day *versus* placebo group as secondary or exploratory/sensitivity endpoints. The SAP will detail which analyses are performed for which treatment groups, and in which cases the LMTM 8 mg/day with placebo comparisons will be provided for which sensitivity, subgroup, and exploratory analyses.

Further analysis on selected primary and secondary endpoints will be provided for pooled LMTM 16 mg/day and 8 mg/day arms compared to placebo. The analysis models will be identical to the 16 mg/day *versus* placebo with the exception of pooled treatment arms. The SAP will detail which analyses are repeated for the pooled 16 mg/day and 8 mg/day arms.

More details about the exact contrast statements used for these tests as well as further sensitivity analyses, additional analyses of the primary variables (such as responder analyses and subgroup analyses), and the analyses of the secondary and exploratory endpoints are described in the subsections below as well as in the SAP.

“Late” starters, *i.e.*, subjects originally randomized to placebo, will be compared to “early” starters, *i.e.*, those originally randomized to LMTM 16 mg/day or 8 mg/day (pooled, and individually for both groups as a sensitivity analysis). The last assessment prior to start of open-label treatment (pre-dose at Visit 7) will serve as the baseline assessment for these comparisons. The analyses will be based on a similar linear mixed model for repeated measures with the aim to investigate whether there is a difference in change in primary and MRI imaging endpoints dependent on LMTM treatment history. The comparison will be implemented through a non-inferiority test.

The non-inferiority margin for the primary endpoint of ADAS-cog11 will be 2 units, motivated by the fact that these 2 units are small compared to the estimated treatment effect of > 5 units (~40% of this effect size). Margins for other endpoints which are exploratory to support a disease modifying argument will be defined in the SAP. The results will also be presented with the Visit 2 Baseline as baseline and treatment visits Week 26 and Week 52 in the open-label, delayed-start phase as Week 78 and Week 104.

## 17.1 Efficacy Endpoints

### 17.1.1 Primary Efficacy Endpoints for Double-Blind Treatment Period

- ADAS-cog11 (LMTM 16 mg/day *versus* placebo)
- ADCS-ADL23 (LMTM 16 mg/day *versus* placebo)

### **17.1.2 Secondary Efficacy Endpoints for Double-Blind Treatment Period**

- Annualized rate of whole brain atrophy on brain MRI using BSI (LMTM 16 mg/day *versus* placebo)
- Difference in temporal lobe F-FDG-PET change in SUVR normalized to pons in subjects with CDR 0.5 at Screening (LMTM 16 mg/day *versus* placebo, and LMTM 8 mg/day *versus* placebo), if a sufficient number of subjects have provided data as specified in the SAP
- ADAS-cog11 and ADCS-ADL23 (LMTM 8 mg/day *versus* placebo)
- Annualized rate of temporal and parietal lobe atrophy on brain MRI using BSI (LMTM 16 mg/day *versus* placebo, and LMTM 8 mg/day *versus* placebo)

### **17.1.3 Secondary Endpoint for Open-Label, Delayed-Start Phase**

- Difference in disease progression on the co-primary clinical endpoints and the MRI imaging endpoint for subjects who started treatment in the double-blind treatment phase and those who started treatment in the open-label, delayed-start phase (referred to as “early” and “late” LMTM starters, respectively)
  - Only ADAS-cog11 will serve as a secondary endpoint; ADCS-ADL23 and other imaging endpoints are exploratory with the aim to be directionally supportive

## **17.2 Number of Subjects and Sample Size Calculation**

The target number of subjects is approximately 450 subjects enrolled in Protocol Version 5.0 and above, randomized in a ratio of 4:1:4 (at the study level) to the LMTM 16 mg/day (200 subjects), LMTM 8 mg/day (50 subjects) and placebo (200 subjects) groups; total enrollment is approximately 500 subjects. Subjects will be assigned to the MMSE severity groups based on screening MMSE score with a target of approximately 2:3:1 (MMSE 16-19, MMSE 20-25, MMSE 26-27 respectively) for those randomized to Protocol Version 5.0 and above. Subjects who drop out after randomization will not be replaced.

Sample size estimations to achieve 90% power (two-sided alpha = 0.05) to detect a difference between LMTM 16 mg/day and placebo (containing intermittent MTC as a urinary discolorant), the primary treatment group comparison in the double-blind treatment period, have been performed for the two co-primary clinical endpoints. These assume a withdrawal rate of 20% to 25% over 52 weeks. The study sample size of approximately 450 subjects (approximately 200 subjects in each treatment group, with a further 50 subjects for secondary analyses of an LMTM 8-mg/day group) is based on the ADCS-ADL23 as a larger sample size is required to achieve the target power.

Based on an estimated decline in ADCS-ADL23 over 52 weeks in the control arm of 7.7 units with an estimated SD of 8.5 units, the study will have >90% power (two-sided alpha=0.05) to detect a reduction in decline of 3.4 units or more. The 3.4 units are motivated by an estimated treatment effect of  $5.0 \pm 1.6$  (mean  $\pm$  standard error) units in the pooled studies TRx-237-005/ TRx-237-015.

Based on an estimated decline in ADAS-cog11 over 52 weeks based on pooled information from Studies TRx-237-005 / TRx-237-015 in the control arm of 6.5 units with an estimated SD of 5.9 units, 200 subjects per treatment arm provide >90% power (two-sided alpha=0.05) to detect a reduction in decline of 2.6 units or more. The 2.6 units represent a conservative value as the estimated treatment effect based on pooled Studies TRx-237-005 / TRx-237-015 is  $5.2 \pm 1.3$  (mean  $\pm$  standard error) units.

With 200 subjects randomized to the primary comparison in the double-blind treatment period under Protocol Version 5.0 and above, 160 to 170 subjects per arm will enter the open-label, delayed-start phase assuming the drop-out rates mentioned above. Assuming a further 10% drop out in the delayed-start phase, the key secondary analysis to demonstrate disease modification by comparing early to late starters with a noninferiority margin of -2 ADAS-cog11 units has approximately 80% power.

Subjects who withdraw from treatment will be encouraged to stay in the study and continue their assessments off-treatment. Subjects' withdrawal rates will be closely monitored in a blinded fashion, to monitor if sample size calculations remain correct.

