
Based on an estimated decline in ADAS-cog11 over 52 weeks based on pooled information from studies TRx-237-005/TRx-237-015 in the control arm of 6.5 units with an estimated SD of 5.9 units, 200 subjects per treatment arm provide >90% power to detect a reduction in decline of 2.6 units or more. The 2.6 units represent a conservative value as the estimated treatment effect based on pooled studies TRx-237-005/TRx-237-015 is <math>5.2 \pm 1.3</math> (mean <math>\pm</math> standard error) units.

With 200 subjects randomized to the primary comparison in the double-blind treatment period under Protocol Version 5.0 and above, 160 to 170 subjects per arm will enter the open-label, delayed-start treatment phase assuming the 20-25% drop-out rates mentioned above. Assuming a further 10% drop out in the delayed-start phase, the key secondary analysis to demonstrate disease modification by comparing early to late starters using a non-inferiority margin of -2 ADAS-cog11 units has approximately 80% power.

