#### **17.4.6 Open-Label, Delayed-Start Analysis**

“Late” starters, *i.e.*, subjects originally randomized to placebo, will be compared to “early” starters, *i.e.*, those originally randomized to LMTM 16 mg/day or 8 mg/day (pooled, and individually for both groups as a sensitivity analysis). The last assessment prior to start of open-label treatment (pre-dose at Visit 7) will serve as the baseline assessment for these comparisons. The analyses will be based on a similar linear mixed model for repeated measures as outlined for the FDA/EMA primary analysis (see model specification in Sections 17.4.2 and 17.4.3) with the aim to investigate whether there is a difference in change in primary and MRI imaging endpoints dependent on LMTM treatment history (certain covariates in the model might be dropped if the model does not converge; see SAP for details).

The comparison will be implemented through a non-inferiority test. The non-inferiority margin for the primary endpoint of ADAS-cog11 will be 2 units, motivated by the fact that these 2 units are small compared to the estimated treatment effect of > 5 units (~40% of this effect size). Margins for other endpoints which are exploratory to support a disease modifying argument will be defined in the SAP.

The results will also be presented with the Visit 2 Baseline as baseline, and treatment visits Week 26 and Week 52 in the open-label, delayed-start phase as Week 78 and Week 104.

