### 5.3. Sample Size Justification

Sample size estimations to achieve 90% power (two-sided alpha = 0.05) to detect a difference between HMTM 16 mg/day and true placebo have been performed for the two co-primary clinical endpoints. These assume a withdrawal rate of 20% to 25% over 52 weeks. The study sample size – here restricted to subjects randomized under protocol version 5.0 or higher as this is the primary analysis population – of approximately 450 subjects (approximately 200 subjects in each treatment group, with a further 50 subjects for secondary analyses of an HMTM 8 mg/day group) is based on the ADCS-ADL23 as a larger sample size is required to achieve the target power.

Based on an estimated decline in ADCS-ADL23 over 52 weeks in the control arm of 7.7 units with an estimated SD of 8.5 units, the study will have approximately 93.2% power (two-sided alpha=0.05) to detect a reduction in decline of 3.4 units or more. The 3.4 units are motivated by an estimated treatment effect of  $5.0 \pm 1.6$  (mean  $\pm$  standard error) units in the pooled studies TRx-237-005/ TRx-237-015.

Based on an estimated decline in ADAS-cog11 over 52 weeks based on pooled information from Studies TRx-237-005 / TRx-237-015 in the control arm of 6.5 units with an estimated SD of 5.9 units, 200 subjects per treatment arm provide approximately 96.7% power (two-sided alpha=0.05) to detect a reduction in decline of 2.6 units or more. The 2.6 units represent a conservative value as the estimated treatment effect based on pooled Studies TRx-237-005 / TRx-237-015 is  $5.2 \pm 1.3$  (mean  $\pm$  standard error) units.

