#### 6.4. Sample Size Justification

With about 400 subjects randomized to control or HMTM 16 mg/day under protocol version 5.0 and above, which is the primary treatment group comparison in the double-blind treatment phase, an estimated 160 to 170 subjects per arm will enter the open-label, delayed-start phase assuming the dropout rates from Section 5.3. Assuming a further 10% drop out in the delayed-start phase, the key secondary analysis to demonstrate disease modification by comparing early to late starters with a noninferiority margin of -2 ADAS-cog11 units has approximately 80% power.

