The analyses will be performed using the restricted maximum likelihood-based MMRM, including the randomization stratification variables (see Section 2.6) as fixed factors, the ADAS-cog11 Baseline-OL value as covariate, and the interaction term between early/ late starters (HMTM treatment history) indicator and visit; with an unstructured covariance matrix and the Kenward and Roger method of calculating the denominator degrees of freedom for the tests of fixed effects. According to the hypotheses, this is a lower-tailed test which will be performed at the alpha=0.025 level of significance.

Sample SAS code (will be fully validated at the analysis stage):

```

PROC MIXED DATA=dataset METHOD=REML COVTEST;
  CLASS subject treatmenthist(REF='Late') visit severity region prioruse;
  MODEL scorediff = treatmenthist/visit severity region prioruse scorew52 / SOLUTION CL
  DDFM=kenwardroger;
  REPEATED visit / SUB=subject TYPE=UN;
  LSMEANS treatmenthist*visit visit / CL;
  LSMESTIMATE treatmenthist*visit "intervention effect at Week 104" 0 1 0 -1 / CL testvalue=2
  LOWER ALPHA=.025;
  *Summary statistics for treatment difference based on LSM
  LSMESTIMATE treatment*visit "intervention effect at Week 78" 1 0 -1 0 / CL testvalue=2 LOWER
  ALPHA=.025;
  RUN;

```

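### At the stated 20–25% dropout, 200 subjects per arm give 150 to 160 entrants to the delayed-start phase, not the 160 to 170 printed in three places

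*Protocol*

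**What the plan says.** Protocol Section 17.2 assigns 200 subjects each to LMTM 16 mg/day and placebo under Protocol Version 5.0 and above. On dropout it says: "These assume a withdrawal rate of 20% to 25% over 52 weeks". It then states that "160 to 170 subjects per arm will enter the open-label, delayed-start phase assuming the drop-out rates mentioned above", adds a further 10% dropout during the delayed-start phase, and gives about 80% power for the key secondary non-inferiority test with a margin of 2 ADAS-cog11 units.

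Two other places repeat the count:
- The Protocol synopsis names the rate in the same sentence: "160 to 170 subjects per arm will enter the open-label, delayed-start treatment phase assuming the 20-25% drop-out rates mentioned above".
- SAP Section 6.4 starts from about 400 subjects in the two arms and writes "an estimated 160 to 170 subjects per arm will enter the open-label, delayed-start phase assuming the dropout rates from Section 5.3". SAP Section 5.3 again gives 20% to 25%.

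The main delayed-start comparison sets late starters (placebo) against early starters, who are "those originally randomized to LMTM 16 mg/day or 8 mg/day (pooled, and individually for both groups as a sensitivity analysis"). SAP Section 6.10 sets the level: "this is a lower-tailed test which will be performed at the alpha=0.025 level of significance".

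**The concern.** All three passages present the count as the result of a stated number randomized and a stated dropout rate, so it can be checked directly, and it fails. The printed lower end of 160 is what the lowest assumed dropout gives, so it is really the upper end. The printed upper end of 170 lies outside the assumption altogether.

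The count is an input to the power statement for the analysis that the documents call key secondary and rely on to demonstrate disease modification. Anyone checking that power starts from it. An overstated count also carries into the number of completers after the further 10% loss.

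**Working it through.** **Inputs.** 200 randomized per arm, dropout *d* = 20% to 25%, further dropout 10%, margin 2 (Protocol Section 17.2; SAP Sections 5.3 and 6.4). One-sided alpha 0.025 (SAP Section 6.10). Primary effects and SDs: 3.4 and 8.5 for ADCS-ADL23, 2.6 and 5.9 for ADAS-cog11 (Protocol Section 17.2, SAP Section 5.3).

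**Step 1: entrants = 200 × (1 − d).**
- d = 20%: 200 × 0.80 = 160
- d = 25%: 200 × 0.75 = 150
- Rate needed for 170: 1 − 170/200 = 15%

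The printed 160 to 170 is therefore not reproduced. Dividing by (1 + d) comes close: 200/1.25 = 160 and 200/1.20 = 166.7. That is not a valid dropout calculation, though it may be where the range came from.

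**Step 2: completers = entrants × 0.90.** 150 → 135, 160 → 144, 170 → 153. The correct range is 135–144 per arm; the printed entrants imply 144–153.

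**Step 3: is the count or the rate wrong?** SAP Section 5.3 gives two primary powers: "the study will have approximately 93.2% power (two-sided alpha=0.05) to detect a reduction in decline of 3.4 units or more" and "200 subjects per treatment arm provide approximately 96.7% power (two-sided alpha=0.05) to detect a reduction in decline of 2.6 units or more". A two-sample t-test, two-sided 0.05, gives:

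| n per arm | ADCS-ADL23 (3.4/8.5) | ADAS-cog11 (2.6/5.9) |
|---|---|---|
| 150 | 93.2% | 96.7% |
| 160 | 94.6% | 97.6% |
| 170 | 95.7% | 98.2% |
| 200 | 97.9% | 99.3% |

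Both stated powers are reproduced at 150 per arm, that is 200 less 25%, and at none of the other counts. Neither document states 150; it is back-solved.

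**Step 4: effect on non-inferiority power.** Assumptions: two-sample t-test on completers, true difference 0, margin 2, one-sided 0.025, and SD 5.9 carried over from the Week 52 calculation. For the pooled comparison, the 8 mg/day arm (50 randomized) has the same dropout, so early starters number 1.25 times late starters.

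| Entrants per 200 | Completers, late arm | 16 mg/day vs control | Pooled early vs late |
|---|---|---|---|
| 150 | 135 | 79.2% | 83.3% |
| 160 | 144 | 81.8% | 85.6% |
| 170 | 153 | 84.0% | 87.6% |

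Moving from the printed to the correct range lowers power by about 2.0 to 2.5 percentage points at each end.

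**Step 5: dependence on the SD.** For 16 mg/day versus control at 135–144 completers, power is 90.6–92.3% for SD 5.0, 79.2–81.8% for SD 5.9, and 64.8–67.6% for SD 7.0.

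**The case against.** Nobody can dispute that 200 × 0.75–0.80 is 150–160. The case on the other side is about weight and remedy.

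- **It is only a planning figure.** No population, test or decision rule uses it, and SAP Version 3.0 (7 June 2023) post-dates the double-blind data snapshot (28 April 2022). This stands: the correction tidies the record and changes no analysis.
- **The rate could be wrong instead of the count.** A 15–20% rate would also remove the conflict. This cannot be excluded from the text alone, but the SAP Section 5.3 powers match 150 per arm, and all three passages take 20–25% as given. That check supports the 25% end only, since the powers fail at 160. It says nothing about what lay behind the delayed-start sentence.
- **Withdrawals may stay on study.** Subjects who stop treatment are encouraged to keep attending visits, and SAP Section 6.1 lets those who are off treatment at Week 52 continue into the second year, so actual entrants could exceed 200 × (1 − d). This does not rescue the range, because each passage presents it as the consequence of the 20–25% rate. Nor would these subjects count in the main non-inferiority population, which requires a dose of open-label drug.
- **The 80% rests on an unstated SD.** This stands. The documents give no SD for the Week 52–104 change, and plausible values move the power far more than the miscount does. The 16 mg-only figures sit closest to 80%, whereas the main comparison is the pooled one.

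**Conclusion.** The error is certain and appears in the Protocol synopsis, Protocol Section 17.2 and SAP Section 6.4. Entrants should read 150–160 per arm, so each printed end is 10 too high: 10/160 = 6% to 10/150 = 7%.

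The effect stops at the count. On an SD of 5.9 and a true difference of 0, about 80% power still holds at the correct numbers, and it fits them slightly better than the printed ones. That reassurance is conditional on the assumed SD. The power figures are also approximate, because the planned mixed model uses Week 78 data as well and the per-protocol open-label population excludes some entrants.

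The 200 per arm, the margin and the test are not called into question by this point. It should be corrected, but it does not threaten the design.

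**What to change.** Replace 160 to 170 with 150 to 160 in the Protocol synopsis, Protocol Section 17.2 and SAP Section 6.4. Leave the 200 per arm, the margin of 2, the test and the statement of about 80% power as they are.

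As a clarification rather than a correction, it would help to state beside the power figure the SD used, the assumed true difference, and whether the 8 mg/day subjects were counted among the early starters.

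The cost is one number range changed in three places, with no effect on sample size, population or analysis. In the SAP it corrects the record of a planning figure only, since the double-blind data had already been analyzed when Version 3.0 was issued.
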